##### **6.2.4.3 Post-Treatment Reaction Assessment**

The Investigator will assess local and systemic reactions post-treatment (within 30-45 minutes after study treatment/EP) and at specified visits. Any reported local post treatment reactions will be graded per the Toxicity Grading Scale for Healthy Adult and Adolescent Volunteers Enrolled in Preventive Vaccine Clinical Trials and any reported systemic post treatment reactions will be graded per CTCAE v4.03 and recorded on the CRFs (see Section 6.6 for more details).

#### **6.2.4.4 Participant Reminder Card**

Subjects will be given an oral thermometer and participant reminder card (PRC) at each study treatment/EP visit. Subjects will be instructed to take and record their temperature daily (at the same time each day). They will also be advised to record local and systemic events on a PRC as shown in Appendix 9.

If Weeks 2, 6, 10 and 12 visits are conducted by telephone, the subject should submit their PRC (i.e. mail, fax, email) to the site personnel prior to the phone visit. If the PRC is not received in advance, site personnel should verbally review all PRC elements listed above. The hard copy of the PRC should be collected at the next in-person study visit. Any entry on PRC determined to meet the criteria for a Grade 1 or higher adverse event should be documented as adverse event. If the PRC entry does not meet the criteria of a Grade 1 or higher AE as per the CTCAE v4.0, clinical judgment can be used to determine whether the entry should be recorded as an AE. For cases where the PRC entry and final AE reporting (i.e., grading) do not agree, the reasoning should be recorded in the source documents.

#### **6.2.4.5 Vital Signs**

Vital signs including body temperature, respiration rate, blood pressure and heart rate will be measured at all the study visits.

#### **6.2.4.6 Weight and Height**

Weight (kg) and height (cm) will be collected at the screening visit. Weight will be collected at each additional visit from Day 0 through discharge.

#### **6.2.4.7 12-lead ECGs**

An ECG will be performed at screening within 30 days of signing of ICF for all subjects to determine subject eligibility. Abnormal ECGs should be interpreted as clinically significant or not clinically significant.

#### **6.2.4.8 Pregnancy Test**

For women of reproductive potential, a negative result for serum pregnancy test (test must have a sensitivity of at least 25 mIU/mL) must be available at the screening visit and urine  $\beta$ -HCG (pregnancy test) prior to each administration of INO-3112 and prior to tumor biopsy collection. If at any point, the  $\beta$ -HCG (pregnancy) test is positive, indicating that the subject is pregnant, no additional study treatment/EP will be administered, but the subject will be followed for the duration of the study and beyond to determine the outcome of the pregnancy (with the subject's consent).

---

#### **6.2.4.9 Laboratory Evaluations**

At screening, blood samples will be collected for serum chemistry and hematology. A urine sample will also be obtained to determine eligibility. At other visits, blood samples will be collected as specified in Table 1 - Schedule of Events. All labs for Day 0 and those associated with any treatment visit should be collected no more than 48 hours prior to treatment and reviewed/evaluated by the PI prior to treatment. Approximately 4 cups of blood will be drawn from each subject during the entire duration of the study.

##### Complete blood count (CBC)

- White blood cell (WBC) count w/ differential
- Red blood cell (RBC) count
- Hemoglobin, Hematocrit
- Platelet count

##### Serum Chemistry

- Glucose
- Albumin
- Total protein
- SGPT (serum glutamic-pyruvic transaminase)/ALT
- SGOT (serum glutamic-oxaloacetic transaminase)/AST
- Alkaline phosphatase
- Bilirubin (total)
- BUN (blood urea nitrogen)
- Calcium
- Creatinine
- Electrolytes (Sodium, Potassium, Chloride, Carbon Dioxide or Bicarbonate)

##### CPK (Creatine Phosphokinase)

##### Serology (required only at screening if serologic test was performed $\geq$ 12 months of informed consent)

- Antibody to HIV
- Hepatitis B surface antigen
- Antibody to Hepatitis C

##### Urinalysis

Urine samples will be tested by dipstick for glucose, protein, and hematuria. If abnormal (presence of protein, hematuria, or glucose  $\geq$  1+) a microscopic examination will be performed.

#### **6.2.4.10 PET/CT Scan**

Baseline PET or CT scan must be performed within 4 weeks prior to Day 0.

The follow-up scan will be performed 3-4 months after Day 0 to evaluate subject disease status. Thereafter, PET/CT scans can be performed 3- 5 months or at study discharge in accordance with local guidelines and institutional practices.

FDG-PET imaging is based on the increased glucose metabolism of tumor cells compared to normal tissue resulting in higher standard uptake volume (SUV). Increased SUVmax at diagnosis has been associated with persistent abnormal FDG uptake after curative chemoradiation and biopsy-proven local recurrence [Kidd 2007]. FDG-PET is already utilized as a follow-up evaluation modality in a variety of cancers, including lymphomas, head and neck cancers, and breast cancer [Schelling 2000, Smith 2000, Weber 2001, Ott 2003, Weber 2003, Brun 2002].

In a prospective study of cervical cancer patients, FDG-PET was demonstrated to be a metabolic biomarker of response and a potential prognostic marker for progression-free survival at 3 years [Schwarz 2007]. A meta-analysis of 16 studies also demonstrated statistical significance for prediction of event-free and overall survival using metabolic response derived from PET and PET/CT imaging [Zhao 2013].

Studies have previously described the abscopal effect of radiation therapy on non-irradiated tumor sites in a variety of cancers [Postow 2012, Prise 2009]. Post-treatment FDG-PET may further provide elucidation of this mechanism by highlighting sites of residual activity. Retrospective and prospective studies have demonstrated that the use of positron emission tomography (PET) with F-18 fluorodeoxyglucose (FDG) in the post-therapy evaluation of patients with cervical carcinoma is predictive of survival outcome [Grigsby 2004, Grigsby 2003].

These studies evaluated patients with similar disease stage to our current investigation and found that SUV PET response at 3 months after chemoradiation correlated with survival and patterns of failure. We propose to describe qualitatively the rates of complete metabolic response (CMR), partial metabolic response (PMR), and progressive disease (PD) in our patient population and compare these rates to patients treated per standard of care in the aforementioned studies to preliminarily explore any differential outcomes.

### **6.3 Study Treatment/EP with INO-3112**

The timing of the first dose will be designated Day 0.

#### **6.3.1 Management of anxiety and pain due to EP procedure**

Subjects will be offered topical anesthetic (e.g. EMLA), to prevent significant discomfort from the study treatment/EP procedure. If EMLA (lidocaine 2.5% and prilocaine 2.5%) is used, an approximately 1.5 cm diameter amount will be applied with occlusion to the site of injection ~30 minutes prior to study treatment/EP.

Subjects may be offered a mild sedative (e.g. 0.5-1 mg lorazepam) for anxiety related to the EP procedure. Mild sedatives may be administered approximately 1 hour prior to EP at Weeks 0, 4, 8 and/or 12. Subjects who receive a mild sedative must not be allowed to operate a motor vehicle for 3-4 hours after receiving medication and must have arranged transportation to depart the study site.

Subjects will be offered an analgesic (e.g. ibuprofen, ketorolac) after study treatment/EP. [Note: The use of any narcotic (including Tylenol with codeine) for pain meets the definition of severe pain (Grade 3) as per the “Guidance for Industry - Toxicity Grading Scale for Healthy Adult and Adolescent Volunteers Enrolled in Preventive Vaccine Clinical Trials, September 2007” (Table 6.1) and therefore do not offer this to the patient unless clinically indicated.]

Subjects who are allergic to or have contraindications to ibuprofen, ketorolac or lorazepam will be offered a suitable alternative.

#### **6.4 Assessment of Clinical Adverse Events**

The injection site will be assessed by study personnel prior to and within 30-45 minutes after study treatment/EP and at next visit prior to study treatment/EP.

Subjects will also be queried regarding the occurrence of any possible adverse events, concomitant medications and new onset chronic disease during their clinic visits. Subjects will be reminded to contact study personnel and immediately report any event that may happen for the duration of the study. These events will be recorded on the subject’s CRF.

At specific visits the Acute Radiation Morbidity Scoring Criteria (RTOG) (Appendix 5) will be used to assess systemic reaction/toxicity/side effects of standard (chemoradiation) therapy.

#### **6.5 Assessment of Laboratory Abnormalities**

Investigators may use clinical judgment to enroll subjects with isolated Grade 1 abnormalities in screening CBC, serum chemistry or CPK values if there is no indication of disease process in the remainder of the history and physical examination.

Blood will be drawn for serum chemistry, hematology and serology assessments as well as pregnancy testing at screening for inclusion into the study as listed in sections 6.2.4.8 and 6.2.4.9.

Urinalysis will be performed at screening to fulfill eligibility criteria. CPK will be performed at Screening and Week 16.

Complete blood count with differential and serum chemistry will be performed at each study treatment/EP and Week 16.

#### **6.6 Assessment of Injection Site Reactions**

When evaluating injection site reactions throughout the study, the investigator will be instructed to use the following grading scale:

**Table 6.1: Grading Scale for Injection Site Reactions**

Local Reaction to Injectable Product (Grade)	Mild(1)	Moderate(2)	Severe(3)	Potentially Life Threatening(4)
Pain	Does not interfere with activity	Repeated use of non-narcotic pain reliever >24 hours or interferes with activity	Any use of narcotic pain reliever or prevents daily activity	Emergency room (ER) visit or hospitalization
Tenderness	Mild discomfort to touch	Discomfort with movement	Significant discomfort at rest	ER visit or hospitalization
Erythema/Redness*	2.5-5 cm	5.1-10 cm	>10 cm	Necrosis or exfoliative dermatitis
Induration/Swelling**	2.5-5 cm and does not interfere with activity	5.1-10 cm or interferes with activity	>10 cm or prevents daily activity	Necrosis

\* September 2007 “FDA Guidance for Industry—Toxicity Grading Scale for Healthy Adult and Adolescent Volunteers Enrolled in Preventive Vaccine Clinical Trials”

\*in addition to grading the measured local reaction at the greatest single diameter, the measurement should be recorded as a continuous variable.

\*\*Induration/Swelling should be evaluated and graded using the functional scale as well as the actual measurement.

## 6.7 Cervical Virologic and Peripheral Blood Immunogenicity Assessment

Whole blood and serum samples to be tested for antibodies to the HPV E6 and E7 proteins and/or T-lymphocytes producing IFN- $\gamma$  will be obtained at baseline (Screening and Day 0 prior to dosing) and at each study treatment/ EP and follow-up visits for the duration of the trial. Other immunological testing may be performed to further define the immune responses to the INO-3112. Details of the immunology sample collection and shipment will be provided in laboratory manual.

Binding antibody responses against HPV E6 and E7 induced by INO-3112 will be measured using ELISA. Commercially available recombinant human HPV-16 and HPV-18 proteins will be used to assess induction of binding antibodies to each of the antigen components.

Using antigen-specific IFN- $\gamma$  ELISpot assays, the number of antigen-specific IFN- $\gamma$ -secreting T-cells in response to stimulation with overlapping peptide libraries spanning consensus antigens HPV16 E6, HPV16 E7, HPV18 E6 and HPV18 E7 will be determined. As previously described [Bagarazzi et al Sci Tran Med]. PBMCs will be incubated with HPV peptide pools at a concentration of 2  $\mu$ g/ml. IFN- $\gamma$  release will be detected after an overnight incubation. Spot forming units (SFU) will be adjusted to  $1 \times 10^6$  PBMCs for each HPV peptide pool.

Flow cytometric assays will be employed to examine any or all of the following characteristics of Study Treatment: induction of T-cells to 1) exhibit phenotypic

markers associated with cytolytic potential after short-term stimulation by HPV antigen (i.e., CTL phenotyping); 2) remain active in the presence of long-term antigen exposure and efficiently synthesize proteins used in lytic activity (i.e., Lytic granule loading); and 3) effectively employ lytic degranulation to drive killing of target cells expressing HPV antigens (i.e., Killing Assay)

1. The CTL phenotyping assay employs short term (4-6 hours) in vitro stimulation of unfractionated PBMC using peptides spanning HPV antigens and appropriate controls. The external cellular markers employed in this assay might include CD3, CD4, CD8 (T-cell identification), CD45RO, CCR7 (memory subset identification) and CD107a (lytic degranulation). The CTL Phenotyping assay may additionally analyze the following intracellular markers: IFN- $\gamma$  (Th1 biasing cytokine), Tumor Necrosis Factor- $\alpha$  (TNF- $\alpha$ ), Granzyme A, Granzyme B and Perforin (involved in lytic degranulation and cytotoxic potential). This panel may vary as additional relevant markers are identified.
2. The lytic granule loading assay employs long term (115-120 hours) in vitro stimulation of unfractionated PBMC using peptides spanning HPV antigens and appropriate controls. The external cellular markers employed in this assay might include CD3, CD4, CD8 (T-cell identification) and CD137 (also known as 41BB, T-cell activation). The Lytic granule loading assay may additionally analyze the following intracellular markers: Granzyme B, Perforin and Granulysin (cytotoxic potential). This panel may vary as additional relevant markers are identified.
3. The killing assay employs long term (115-120 hours) in vitro stimulation of unfractionated PBMC using peptides spanning HPV antigens. After the initial long term incubation, stimulated whole PBMC or CD8+ T-cells (hereafter referred to as Effector Cells) are co-incubated for ~1 hr with target cells treated with a stain (Target Stain) that differentiates them from Effector Cells and have additionally been pulsed with a substrate reagent which is activated only by the activity of Granzyme B or a substrate which is activated by the activity of terminal caspases involved in the induction and perpetuation of apoptosis. Enumeration of target cells identified by the Target Stain and the presence of an active substrate reagent within the Target population represents a measure of a functional T cell response that is capable of Target cell killing.

A standardized binding ELISA will be performed to measure the anti-HPV16/HPV-18 E6 or E7 antibody response induced by INO-3112. 96-well enzyme immunoassay plates will be coated with HPV16 or HPV18 E6 or E7 proteins (1  $\mu$ g/ml).

PBMC responses against a pool of known antigenic epitopes pooled from Cytomegalovirus, Epstein Barr Virus and Influenza (CEF) will be tested in order to track general cellular immune competence during the study. Assessment of the

response to these reference antigens that are not related to the study antigens will give a baseline reading of immunocompetency at study entry. Observation for variation of response against these reference antigens during the progression of study treatment may therefore give insight as to general immune competency and aid in accounting for variation in response against study antigens encoded by INO-3112 in the same manner as HPV response described above.

#### Cervical Virologic Assessment

Subjects must have positive HPV-16 and/or HPV-18 genotype result from ISH or PCR assays at screening or prior to screening for inclusion in the study. Subjects whose specimens also test positive for other HPV genotypes are not excluded as long as they have a positive result for HPV 16 and/or HPV 18. If a subject has documented evidence of HPV-16 and/or HPV-18 infection results from cervical specimen obtained prior to anti-cancer treatment, then those results will be eligible for inclusion in the study.

If applicable, a liquid based cytology sample (ThinPrep™) will be collected for HPV PCR at screening and at Weeks 16 and 36. Samples will be sent to a central laboratory to be analyzed for the presence of HPV infection by PCR.

#### Cervical Immunologic Assessment

If applicable, two Digene cervical brushes will be collected at baseline (screening and Day 0), Weeks 16 and 36 and will be banked and frozen for immunological testing.

Tissue specimens obtained as routine diagnostic and therapeutic specimens will be analyzed to characterize the presence, density, and co-localization of immune cell subsets, including macrophages, dendritic cells, T cells (CD8 and regulatory T cells), and NK cells. As tissue availability permits, the specimens will also be analyzed for cytokine expression.

At visits where multiple cervical samples are collected, the two Digene cervical brushes will be collected prior to the ThinPrep™ sample.

If adequate residual specimen is available, immunohistochemistry (IHC) studies will be performed on either tumor tissue block or unstained slides from tumor(s) from the following time points: (1) at screening; (2) at Week 16 (one month post-dose 4).

A tumor biopsy will be used to investigate the post-radiation changes at a cellular level, with particular focus on the presence and populations of immune cells to compare to pre radiation characterization.

Characterization of the various cell populations present in the primary tumor site will allow for elucidation of long-term effects of radiation-induced changes, potential cell-mediating killing in microscopic colonies of residual tumor, and mechanisms of immune cell interactions in the post-radiation setting. The maturation and clonal expansion of T cells in response to repeated immunotherapy should result in the production of a memory T cell subset in the immune cell population.

---

Biopsy samples can also be compared to the post-dose peripheral blood samples to study shifts in cell populations or HPV-specific proliferative response. In addition, biomarkers may be identified as predictors of early response, resistance, or recurrence, and contribute to patient outcome stratification.

### **6.8 Disease Status**

Diseases status will be determined based on RECIST (version 1.1). Disease status should be categorized into:

1. No evidence of disease (NED)
2. Partial Response
3. Stable disease
4. Progressive disease

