Cohort 1: Subjects in Cohort 1 can be screened either prior to initiation of chemoradiation, or during chemoradiation and should be enrolled such that their first study treatment (Day 0) will be delivered within 2 weeks of completing their chemoradiation therapy;

Cohort 2: Subjects in Cohort 2 can be screened and enrolled such that their first study treatment (Day 0) is no sooner than 2 weeks and no later than 4 weeks after completing the salvage therapy. If in the

- 
- investigators opinion, there are no additional salvage therapy options, the subject may be enrolled in Cohort 2 without having received salvage therapy immediately prior to enrollment.
- a Procedures and visits scheduled from Day 0 through Wk 16 must occur  $\pm$ 1 week of scheduled time. Procedures and visits scheduled from Week 24 to Week 36 must occur  $\pm$  2 weeks of scheduled time.
- b assessment to be performed if visit done as phone-call
- c Targeted physical examination at all visits except full examination at screening (includes complete gynecological exam) and discharge visit
- d Disease status should be categorized into 1) No evidence of disease (NED) 2) Partial Response 3) Stable disease 4) Progressive disease
- e Temperature, respiratory rate, blood pressure, heart rate, weight and height. Height collected at screening only
- f Paraffin embedded tissue obtained for diagnosis of cervical cancer must be available for HPV testing
- g Serum chemistry includes glucose, albumin, total protein, SGPT, SGOT, alkaline phosphatase, total bilirubin, blood urea nitrogen (BUN), calcium, creatinine, electrolytes (sodium, potassium, chloride, carbon dioxide or bicarbonate)
- h Urine samples will be tested by dipstick for glucose, protein, and hematuria.
- i Serum pregnancy test required at screening. Urine pregnancy test should be used prior to tumor biopsy and prior to each study treatment/EP
- j At least 34 mL (4 x 8.5 mL tubes) whole blood in Acid Citrate Dextrose tubes and 4 mL serum per time point. A total of at least 68 mL whole blood and 4 mL serum should be collected prior to dosing on Day 0
- k Assessed 30 to 45 minutes after study treatment/EP and at post-treatment visits
- l A tumor biopsy collection is required at screening if residual tissue and/or unstained slides are not available

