### **8.4 Analysis of Clinical Responses**

Disease status frequencies based on RECIST criteria categories will be summarized.

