### 13.10 Appendix 10: RECIST

- A. Response will be evaluated in this study using the international criteria proposed by the Response Evaluation Criteria in Solid Tumors (RECIST) guideline (version 1.1). Changes in the largest diameter (unidimensional measurement) of the tumor lesions and the shortest diameter in the case of malignant lymph nodes are used in the RECIST criteria:

i. Definitions

Evaluable for Target Disease response: Only those participants who have measurable disease present at baseline, have received at least one cycle of therapy, and have had their disease re-evaluated will be considered evaluable for target disease response. These participants will have their response classified according to the definitions stated below. (Note: Participants who exhibit objective disease progression prior to the end of cycle 1 will also be considered evaluable.)

Evaluable Non-Target Disease Response: Participants who have lesions present at baseline that are evaluable but do not meet the definitions of measurable disease, have received at least one cycle of therapy, and have had their disease re-evaluated will be considered evaluable for non-target disease. The response assessment is based on the presence, absence, or unequivocal progression of the lesions.

ii. Disease Parameters

Measurable disease. Measurable lesions are defined as those that can be accurately measured in at least one dimension (longest diameter to be recorded) as  $\geq 20$  mm by chest x-ray or  $\geq 10$  mm with CT scan, MRI, or calipers by clinical exam. All tumor measurements must be recorded in millimeters (or decimal fractions of centimeters).

Malignant lymph nodes. To be considered pathologically enlarged and measurable, a lymph node must be  $\geq 15$  mm in short axis when assessed by CT scan (CT scan slice thickness recommended to be no greater than 5 mm). At baseline and in follow-up, only the short axis will be measured and followed.

Non-measurable disease. All other lesions (or sites of disease), including small lesions (longest diameter  $< 10$  mm or pathological lymph nodes with  $\geq 10$  to  $< 15$  mm short axis), are considered non-measurable disease. Bone lesions, leptomeningeal disease, ascites, pleural/pericardial effusions, lymphangitis cutis/pulmonitis, inflammatory breast disease, abdominal masses (not followed by CT or MRI), and cystic lesions are all considered non-measurable.

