### iii. Response Criteria

Complete Response (CR): Disappearance of all target lesions. Any pathological lymph nodes (whether target or non-target) must have reduction in short axis to <10 mm.

Partial Response (PR): At least a 30% decrease in the sum of the diameters of target lesions, taking as reference the baseline sum diameters.

Progressive Disease (PD): At least a 20% increase in the sum of the diameters of target lesions, taking as reference the smallest sum on study (this includes the baseline sum if that is the smallest on study). In addition to the relative increase of 20%, the sum must also demonstrate an absolute increase of at least 5 mm. (Note: the appearance of one or more new lesions is also considered progressions).

Stable Disease (SD): Neither sufficient shrinkage to qualify for PR nor sufficient increase to qualify for PD, taking as reference the smallest sum diameters while on study.

iv. Evaluation of Non-Target Lesions

Complete Response (CR): Disappearance of all non-target lesions and normalization of tumor marker level. All lymph nodes must be non-pathological in size (<10 mm short axis).

Note: If tumor markers are initially above the upper normal limit, they must normalize for a patient to be considered in complete clinical response.

Non-CR/Non-PD: Persistence of one or more non-target lesion(s) and/or maintenance of tumor marker level above the normal limits.

Progressive Disease (PD): Appearance of one or more new lesions and/or *unequivocal progression* of existing non-target lesions. *Unequivocal progression* should not normally trump target lesion status. It must be representative of overall disease status change, not a single lesion increase.

Although a clear progression of “non-target” lesions only is exceptional, the opinion of the treating physician should prevail in such circumstances, and the progression status should be confirmed at a later time by the review panel (or Principal Investigator).

v. Evaluation of New Lesions

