**Time point response: patients with non-target disease only**

Non-Target Lesions	New Lesions	Overall Response
CR	No	CR
Non-CR/non-PD	No	Non-CR/non-PD*
Not all evaluated	No	not evaluated
Unequivocal PD	Yes or No	PD
Any	Yes	PD
* 'Non-CR/non-PD' is preferred over 'stable disease' for non-target disease since SD is increasingly used as an endpoint for assessment of efficacy in some trials so to assign this category when no lesions can be measured is not advised		

vii. Confirmation/Duration of Response

**Confirmation:** Confirmation of PR and CR is required to ensure responses identified are not the results of measurement error. This will also permit appropriate interpretation of results in the context of historical data where response has traditionally required confirmation.

**Duration of overall response:** The duration of overall response is measured from the time measurement criteria are met for CR or PR (whichever is first recorded) until the first date that recurrent or progressive disease is objectively documented (taking as reference for progressive disease the smallest measurements recorded on study)

Duration of overall complete response: The duration of overall CR is measured from the time measurement criteria are first met for CR until the first date that recurrent disease is objectively documented.

Duration of stable disease: Stable disease is measured from the start of the treatment until the criteria for progression are met, taking as reference the smallest sum on study (if baseline sum is the smallest, this is the reference for calculation of PD).

- B. Progression Free Survival**- any progression of disease as defined below will be recorded and summarized for subjects in the individual cohorts and overall

Overall Survival: Overall Survival (OS) is defined as the time from randomization (or registration) to death due to any cause, or censored at date last known alive.

Progression-Free Survival: Progression-Free Survival (PFS) is defined as the time from randomization (or registration) to the earlier of progression or death due to any cause. Participants alive without disease progression are censored at date of last disease evaluation.

Time to Progression: Time to Progression (TTP) is defined as the time from randomization (or registration) to progression, or censored at date of last disease evaluation for those without progression reported

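### The four disease-status codes leave stable disease as the only code for persistent non-target-only disease, against Appendix 10's advice, and NED merges on-study clearance with no disease before dosing

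*Combined protocol and SAP*

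**What the plan says.** Section 6.8 opens with "Diseases status will be determined based on RECIST (version 1.1") and then restricts the status to four categories. Table 1 footnote d gives the same list: "Disease status should be categorized into 1) No evidence of disease (NED) 2) Partial Response 3) Stable disease 4) Progressive disease".

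Appendix 10 is wider. It provides for subjects who "have lesions present at baseline that are evaluable but do not meet the definitions of measurable disease", and gives them their own time point table with four outcomes: CR, Non-CR/non-PD, not evaluated and PD. Stable disease is not among them. Non-CR/non-PD is defined as "Persistence of one or more non-target lesion(s) and/or maintenance of tumor marker level above the normal limits". The table's footnote says that this label "is preferred over 'stable disease' for non-target disease" and adds that "to assign this category when no lesions can be measured is not advised".

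Section 8.4 consists of one sentence: "Disease status frequencies based on RECIST criteria categories will be summarized". It names no categories, no split by baseline disease and no denominator. Section 4.1 does not make measurable disease a condition of entry.

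**The concern.** Two documented rules give different codes for the same subject. Section 6.8 and footnote d tell the site what to record; Appendix 10 tells it how to assess. Where they differ, the recorded code decides what 8.4 can show.

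The affected subjects are plausible here. Cohort 1 enters within two weeks of curative-intent chemoradiation, when what remains may be small. Appendix 10 treats lesions under 10 mm and nodes of 10 to under 15 mm as non-measurable. A table that shows such subjects as stable implies a measured lack of change that was never measured.

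NED raises a second problem. If women already clear of disease before the first dose appear as NED at Week 16, they sit in the same row as subjects whose lesions disappeared after dosing. A reader of the 8.4 table could take the whole row as response.

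**Working it through.** The plan states no figure on this point, so the check is mainly a comparison of texts.

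**Step 1: map the Appendix 10 outcomes to the 6.8 codes.** NED is not defined in 6.8; I assume that it is the intended home for CR.

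| Appendix 10 outcome | Code in 6.8 / footnote d |
|---|---|
| CR | NED (assumed) |
| PR | Partial response |
| SD | Stable disease |
| PD | Progressive disease |
| Non-CR/non-PD | none |
| Not evaluated | none |

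Four of the six have a counterpart; two do not.

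**Step 2: follow a subject with non-target disease only.**
- Lesions all gone: CR, so NED. No problem.
- Unequivocal progression or a new lesion: PD. No problem.
- Not all lesions evaluated: no code. Section 8.6 says that missing data are not imputed, so the subject can be left missing.
- Lesions persist without progression: Non-CR/non-PD, no code. NED is wrong because disease is present. PR is wrong because it needs a 30% fall in the target-lesion sum, and there are no target lesions. PD is wrong because there is no progression. Stable disease is all that is left.

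**Step 3: check NED against baseline.** In Appendix 10, CR is the disappearance of lesions, so lesions must have been present. NED has no such condition. Table 1 records disease status at screening and next at Week 16, with nothing at Day 0. Section 6.1.1 lets Cohort 1 be screened before or during chemoradiation, so screening status may predate the effect of that treatment. The PET/CT within 4 weeks before Day 0 (Table 1 footnote n) is the closest record of disease at the first dose.

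**Step 4: size.** Section 8.1 uses n=10. One subject recoded moves a category by 1/10 = 10 percentage points. Let k be the number of subjects with persistent non-target-only disease; the documents do not give it. As an illustration, assume that 2 of 10 subjects are truly stable on measurable disease, with exact 95% intervals for scale:

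| k | Shown as stable | Exact 95% interval |
|---|---|---|
| 0 | 2/10 = 20% | 2.5% to 55.6% |
| 1 | 3/10 = 30% | 6.7% to 65.2% |
| 3 | 5/10 = 50% | 18.7% to 81.3% |
| 5 | 7/10 = 70% | 34.8% to 93.3% |

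The denominator matters less: dropping one unevaluated subject turns 2/10 = 20.0% into 2/9 = 22.2%.

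**The case against.** The strongest reply is that 8.4 refers to RECIST categories and does not cite the four-item list. Section 6.8 itself starts from RECIST 1.1, and Appendix 10 already separates target from non-target disease. On that reading 6.8 is shorthand and Appendix 10 governs. This is a fair reading of 8.4. It does not help at the point of recording: 6.8 and footnote d state the categories to be used, and a status recorded as stable cannot later be split without going back to the lesion data. The CRF is not among the documents, so whether it follows the four-item list is an inference.

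It can also be said that Appendix 10 only prefers one label and advises against the other, that its reason is the use of stable disease as an efficacy endpoint in some trials, and that clinical outcomes here are exploratory with no test or threshold. All of that stands. It limits the consequence but does not remove the conflict.

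On NED, the screening status and the baseline PET/CT could identify some women who were clear beforehand. The scan can; the screening status often cannot, for the reason in step 3. Nothing in 8.4 tells the analyst to use either.

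**Conclusion.** The concern holds in a limited form. Under the stated codes, persistent, non-progressing, non-target-only disease can be recorded only as stable disease, which Appendix 10 advises against. NED does not distinguish clearance on study from absence of disease before the first dose. Each affected subject moves a row of the 8.4 table by 10 percentage points at n=10. How many there will be is unknown. The result assumes that NED stands for CR and that sites record the categories that 6.8 states.

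A reader might infer more, and the documents do not support it:
- Not all non-measurable disease is forced into stable disease; clearance and progression still have codes.
- The absent code for not evaluated misclassifies nobody. It leaves a gap and an unstated denominator.
- The 8.4 frequencies are not the only clinical summary. Appendix 10 part B summarizes progression by cohort and overall, and Section 6.2.4.10 describes metabolic response rates. Neither depends on the stable disease code.
- No size per cohort is given, so no shift per cohort can be stated.

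**What to change.** In 6.8, Table 1 footnote d and any matching CRF field, replace the four codes with the Appendix 10 outcomes: CR, PR, SD, PD, Non-CR/non-PD and not evaluated. Add a code for no disease at baseline, assigned from the PET/CT taken within 4 weeks before Day 0. For Cohort 1, record that scan's date relative to the end of chemoradiation: Day 0 falls within 2 weeks of completion, so a scan 4 weeks earlier was taken at least 4 − 2 = 2 weeks before treatment ended. Section 3 gives a different window for the same scan (1 to 2 weeks before Day 0); the two statements need reconciling, and the coding rule works with either.

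In 8.4, list the categories, tabulate them by baseline disease (measurable, non-measurable only, none), and state whether subjects who were not evaluated stay in the denominator. With about 10 subjects this is a small table of counts.

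The cost is a code list and a table shell. Fewer subjects may be shown as stable or NED.
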